3.1 Registration (STEP 1)

Rev. 7/12 3.1.1 Patients (male or female) must be older than 18 years and must have an intact *primary* (not recurrent) invasive carcinoma of the breast. Biopsy confirmation of the primary tumor should be by needle biopsy (preferred); incisional surgical biopsy is allowed as long as there is residual palpable or imageable tumor in the breast.

3.1.2 Patients with synchronous contralateral invasive breast cancer are excluded.

Rev. 7/12 3.1.3 Patients should have at least one organ system involved with distant metastatic disease. If only a single metastatic lesion is present, biopsy is mandatory. See Section [6](#)

Rev. 4/14 3.1.4 Baseline studies must be performed 8 weeks prior to the start of systemic therapy, and must document the extent of disease in the breast; the specifics of this are at physician discretion, but must address clinical signs and symptoms (see Section 7.1). If pre-therapy scans were not performed, scans performed within the first 4 weeks

of systemic therapy, but prior to registration, will be accepted. Radiology reports documenting status of disease must be available.

Rev. 4/14 3.1.5 If palliative radiation to non-breast sites is required prior to initiation of systemic therapy, scans may be completed within 8 weeks prior to or 4 weeks following the start of radiation therapy.

Rev. 7/12 3.1.6 If patient has only one metastatic lesion/focus, this must be proven by biopsy and the pathology report confirming the diagnosis of primary breast cancer, as well as the metastatic site, must be available.
Single metastatic lesion? _____ (Yes/No) Biopsy? _____ (Yes/No)

Rev. 7/12 3.1.7 Patients may have had prior non-invasive (DCIS) cancer if there has been no recurrence; prior ipsilateral invasive cancer also allowed if more than 5 years previous.

 3.1.8 Patients with a history of other primary cancers are eligible if the pathology report confirming the diagnosis of primary breast cancer is available and the other primary cancer was curatively treated with a 5-year disease-free interval.

Rev. 4/15 3.1.8.1 Patients with non-melanoma skin cancer are eligible; however, patients with squamous cell carcinoma of other sites (except in-situ cervix) are not eligible.

 3.1.9 Women of childbearing potential and sexually active males must be strongly advised to use an accepted and effective method of contraception.

 3.1.10 Patients with CNS metastases are eligible (as long as projected survival is > 6 months).

Rev. 7/12, 7/13 3.1.11 Patients who require radiotherapy to distant metastases during induction systemic therapy are eligible.

3.2 Randomization (STEP 2)

Rev. 7/12, 4/15 3.2.1 Date of randomization must be within 32 weeks of initiation of optimal systemic therapy.

Rev. 7/12 3.2.2 Patients must have completed at least 16 weeks of optimal systemic therapy (appropriate to the tumor biological profile and the patient's age and menopausal status).

NOTE: The patient will be considered eligible if the last day of the treatment cycle meets the 16 weeks criteria. For example, the last chemotherapy dose might be administered in week 15, while the cycle might end in week 16 or 17. In this case, the patient will be considered eligible for the study.

Rev. 7/12, 7/13 3.2.2.1 If systemic therapy is discontinued for toxicity, there is no distant progression and at least 12 weeks of therapy have been delivered, then the patient remains eligible. If systemic therapy is changed for reasons other than progression of disease (e.g. from chemotherapy to endocrine therapy), the patient remains eligible.

Rev. 7/12, 2/13
4/14

Rev. 4/14

Rev. 7/12

3.2.3 Documentation regarding the details of administration of all systemic chemotherapy must be available.

3.2.4 Patients must not have experienced distant disease progression since the start of systemic therapy, as evidenced by clinical and radiographic documentation of disease status before treatment and within 6 weeks prior to randomization, including:

- a. No new sites of disease
- b. No enlargement of existing sites by 20% or more in longest diameter
- c. No symptomatic deterioration
- d. Imaging at step 2 should preferably be the same as at Step 1 (baseline). It must address all previous sites of disease and all clinical signs and symptoms. If all Step 1 imaging tests cannot be repeated, the reason should be documented (e.g. declined by insurance). Step 2 imaging must evaluate all known sites of disease and address all signs/symptoms present at Step 2.

3.2.5 Patients must be judged to be candidates for complete resection with free margins followed by radiation therapy (if radiation therapy is indicated).

3.2.6 Local disease at the primary site must be asymptomatic.

3.2.7 Patients must have adequate organ function to undergo local therapy 4 weeks +/- 2 weeks prior to randomization per investigator discretion and institutional guidelines.

3.2.7.1 [Removed in Addendum #2]

3.2.7.2 [Removed in Addendum #2]

3.2.7.3 [Removed in Addendum #2]

3.2.7.4 [Removed in Addendum #2]

3.2.7.5 [Removed in Addendum #2]

3.2.8 Women must not be pregnant or breast-feeding due to toxicity of systemic therapy and radiotherapy to fetus/infant.

All females of childbearing potential must have a blood test or urine study within 2 weeks prior to randomization to rule out pregnancy.

Female? _____ (Yes/No)

Date of blood test or urine study: _____

Physician Signature

Date

OPTIONAL: This signature line is provided for use by institutions wishing to use the eligibility checklist as source documentation.

4. Registration Procedures

CTEP Investigator Registration Procedures

Food and Drug Administration (FDA) regulations and National Cancer Institute (NCI) policy require all investigators participating in any NCI-sponsored clinical trial to register and to renew their registration annually.

Registration requires the submission of:

- a completed **Statement of Investigator Form** (FDA Form 1572) with an original signature
- a current Curriculum Vitae (CV)
- a completed and signed **Supplemental Investigator Data Form** (IDF)
- a completed **Financial Disclosure Form** (FDF) with an original signature

Fillable PDF forms and additional information can be found on the CTEP website at <http://ctep.cancer.gov/investigatorResources/investigator_registration.htm>. For questions, please contact the **CTEP Investigator Registration Help Desk** by email at <[contact]>.

CTEP Associate Registration Procedures / CTEP-IAM Account

The Cancer Therapy Evaluation Program (CTEP) Identity and Access Management (IAM) application is a web-based application intended for use by both Investigators (i.e., all physicians involved in the conduct of NCI-sponsored clinical trials) and Associates (i.e., all staff involved in the conduct of NCI-sponsored clinical trials).

Associates will use the CTEP-IAM application to register (both initial registration and annual re-registration) with CTEP and to obtain a user account.

Investigators will use the CTEP-IAM application to obtain a user account only. (See CTEP Investigator Registration Procedures above for information on registering with CTEP as an Investigator, which must be completed before a CTEP-IAM account can be requested.)

An active CTEP-IAM user account will be needed to access all CTEP and CTSU (Cancer Trials Support Unit) websites and applications, including the CTSU members' website.

Additional information can be found on the CTEP website at <http://ctep.cancer.gov/branches/pmb/associate_registration.htm>. For questions, please contact the **CTEP Associate Registration Help Desk** by email at <[contact]>.

CTSU Registration Procedures

This study is supported by the NCI Cancer Trials Support Unit (CTSU).

Each investigator or group of investigators at a clinical site must obtain IRB approval for this protocol and submit IRB approval and supporting documentation to the CTSU Regulatory Office before they can be approved to enroll patients. Study centers can check the status of their registration packets by querying the Regulatory Support System (RSS) site registration status page of the CTSU member web site by entering credentials at <https://www.ctsu.org>. For sites under the CIRB initiative, IRB data will automatically load to RSS.

Downloading Site Registration Documents:

Site registration forms may be downloaded from the **E2108** protocol page located on the CTSU members' website.

- Go to <https://www.ctsu.org> and log in to the members' area using your CTEP-IAM username and password
- Click on the Protocols tab in the upper left of your screen
- Click on the **ECOG-ACRIN** link to expand, then select trial protocol **E2108**
- Click on the Site Registration Documents link

Requirements for E2108 site registration:

- CTSU IRB Certification (for sites not participating via the NCI CIRB)
- CTSU IRB/Regulatory Approval Transmittal Sheet (for sites not participating via the NCI CIRB)

Submitting Regulatory Documents

Submit completed forms along with a copy of your IRB Approval *and Model Informed Consent* to the CTSU Regulatory Office, where they will be entered and tracked in the CTSU RSS.

CTSU Regulatory Office
[name]
[name]
[contact]
[contact]
E-mail: [contact] (for regulatory document submission only)

Required Protocol Specific Regulatory Documents

1. CTSU Regulatory Transmittal Form.
2. Copy of IRB Informed Consent Document.

NOTE: Any deletion or substantive modification of information concerning risks or alternative procedures contained in the sample informed consent document must be justified in writing by the investigator and approved by the IRB.

3. A. CTSU IRB Certification Form.
Or
B. Signed HHS OMB No. 0990-0263 (replaces Form 310).
Or
C. IRB Approval Letter

NOTE: The above submissions must include the following details:

- Indicate all sites approved for the protocol under an assurance number.
- OHRP assurance number of reviewing IRB
- Full protocol title and number
- Version Date

- **Type of review (full board vs. expedited)**
- **Date of review.**
- **Signature of IRB official**

Checking Your Site's Registration Status:

Check the status of your site's registration packets by querying the RSS site registration status page of the members' section of the CTSU website. (Note: Sites will not receive formal notification of regulatory approval from the CTSU Regulatory Office.)

- Go to <https://www.ctsu.org> and log in to the members' area using your CTEP-IAM username and password
- Click on the Regulatory tab at the top of your screen
- Click on the Site Registration tab
- Enter your 5-character CTEP Institution Code and click on Go

Patient Enrollment

Patient registration can occur only after pre-treatment evaluation is complete, eligibility criteria have been met, and the study site is listed as 'approved' in the CTSU RSS. Patients must have signed and dated all applicable consents and authorization forms.

Patient enrollment will be facilitated using the Oncology Patient Enrollment Network (OPEN). OPEN is a web-based registration system available on a 24/7 basis. To access OPEN, the site user must have an active CTEP-IAM account (check at <<https://eapps-ctep.nci.nih.gov/iam/index.jsp>>) and a 'Registrar' role on either the LPO or participating organization roster.

All site staff will use OPEN to enroll patients to this study. It is integrated with the CTSU Enterprise System for regulatory and roster data. OPEN can be accessed at <https://open.ctsu.org> or from the OPEN tab on the CTSU members' side of the website at <https://www.ctsu.org>.

Prior to accessing OPEN site staff should verify the following:

- All eligibility criteria has been met within the protocol stated timeframes.
- All patients have signed an appropriate consent form and HIPAA authorization form (if applicable).

NOTE: The OPEN system will provide the site with a printable confirmation of registration and treatment information. Please print this confirmation for your records.

Further instructional information is provided on the OPEN tab of the CTSU members' side of the CTSU website at <https://www.ctsu.org> or at <https://open.ctsu.org>. For any additional questions contact the CTSU Help Desk at [name] or [contact].

4.1 Registration (Step 1)

Rev. 7/12

Patients may register to Step 1 at any time prior to the start of systemic therapy or < 30 weeks after the start of systemic therapy, with randomization to step 2 no earlier than 16 weeks after start of systemic therapy (once response or stable disease is documented).

Rev. 7/12

[Note deleted in Addendum #2]

The following information will be requested:

4.1.1 Protocol Number

4.1.2 Investigator Identification

 4.1.2.1 Institution and affiliate name

 4.1.2.2 Investigator's name

4.1.3 Patient Identification

 4.1.3.1 Patient's initials and chart number

 4.1.3.2 Patient's Social Security number

 4.1.3.3 Patient demographics

 4.1.3.3.1 Sex

 4.1.3.3.2 Birth date

 4.1.3.3.3 Race

 4.1.3.3.4 Ethnicity

 4.1.3.3.5 Nine-digit ZIP code

 4.1.3.3.6 Method of payment

4.1.4 Eligibility Verification

Patients must meet all of the eligibility requirements listed in Section 3. An eligibility checklist has been appended to the protocol. A confirmation of registration will be forwarded by the ECOG-ACRIN Operations Office - Boston.

4.1.5 Additional Requirements

4.1.5.1 Patients must provide a signed and dated, written informed consent form.

NOTE: Copies of the consent are not collected by the ECOG-ACRIN Operations Office - Boston.

Rev. 7/12, 2/13

4.1.5.2 Pathology materials and blood samples submitted as indicated in Section 9 for banking per patient consent.

NOTE: ECOG-ACRIN requires that biological samples submitted from patients participating in E2108 be entered and tracked via the online ECOG-ACRIN Sample Tracking System (STS). Any case reimbursements associated with sample

submissions must not be captured if samples are not logged into STS. See Section [9.3](#)

NOTE: Institutions outside of the United States and Canada must confer with the receiving laboratory and the ECOG-ACRIN Operations Office - Boston regarding logistics for submission of fresh samples.

4.2 Randomization (Step 2)

Rev. 7/12

Randomization to step 2 is to occur within 16 to 32 weeks after start of systemic therapy (once response or stable disease is documented).

Rev. 7/12

Step 2 treatment must not start prior to randomization and must start after completion of at least 16 weeks of systemic therapy and no more than 32 weeks from start of systemic therapy.

The following information will be requested:

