
For non-clinical questions (i.e. unrelated to patient eligibility, treatment, or clinical data submission) contact the CTSU Help Desk by phone or e-mail: CTSU General Information Line – [name], or [contact]. All calls and correspondence will be triaged to the appropriate CTSU representative.
		

For detailed information on the regulatory and monitoring procedures for CTSU sites please review the CTSU Regulatory and Monitoring Procedures policy located on the CTSU members' website education and resources tab > CTSU Operations Information > CTSU Regulatory and Monitoring Policy">https://www.ctsu.org > education and resources tab > CTSU Operations Information > CTSU Regulatory and Monitoring Policy
		

The CTSU Web site is located at https://www.ctsu.org
		

Schema

Rev. 7/13 Accrual = 368

1. Women with intact primary tumors AND metastatic disease at any site are eligible.
2. Patients may register (Step 1) at anytime following the diagnosis of Stage IV breast cancer, either before or after the start of systemic therapy, up to the 30th week of treatment.
3. Patients must be randomized (Step 2) within 32 weeks after the start of systemic therapy.
4. Patients may not be randomized (Step 2) less than 16 weeks after the start of systemic therapy.
5. At the time of randomization, patients must have documentation of CR, PR or SD as response to optimal systemic therapy.
6. Early local therapy (Arm B) is defined as surgery and radiotherapy for the primary tumor, following induction systemic therapy. Surgery is to occur no later than 10 weeks after randomization.
7. Continued systemic therapy is defined as therapy delivered only as needed for control of distant disease.
8. All randomized patients will be followed for treatment and disease status for 5 years post randomization.
9. Patients who are not randomized will be followed for survival for 5 years post registration.

1. Introduction

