2.2 Secondary Objectives

Rev. 4/14

- 2.2.1 To compare the time to uncontrolled chest wall disease between patients who receive early local therapy versus patients who receive palliative local therapy
- 2.2.2 To determine whether there is a difference in HRQL between patients who receive early local therapy and those who receive palliative local therapy.
- 2.2.3 To determine whether the absolute value of the CTC burden at six months following randomization will be lower in Arm B than Arm A and whether this value is inversely related to survival.
- 2.2.4 To collect tumor and blood specimens for future exploration of the biological interactions between the primary tumor and metastatic lesions and the effect of primary tumor resection.

3. Selection of Patients

Each of the criteria in the checklist that follows must be met in order for a patient to be considered eligible for this study. Use the checklist to confirm a patient's eligibility. For each patient, this checklist must be photocopied, completed and maintained in the patient's chart.

In calculating days of tests and measurements, the day a test or measurement is done is considered Day 0. Therefore, if a test is done on a Monday, the Monday four weeks later would be considered Day 28.

ECOG-ACRIN Patient No. _____

Patient's Initials (L, F, M) _____

Physician Signature and Date _____

NOTE: All questions regarding eligibility should be directed to the study chair or study chair liaison.

NOTE: Institutions may use the eligibility checklist as source documentation if it has been reviewed, signed, and dated prior to randomization by the treating physician.

Rev. 7/12 **NOTE:** Patients may register (Step 1) at any time from the time of diagnosis of stage IV breast cancer (if eligibility criteria met) to the time when a maximum of 30 weeks of induction systemic therapy has been completed. (Induction systemic therapy includes chemotherapy, endocrine therapy, bone-specific agents, and biologic therapy.)

Rev. 7/13 **NOTE:** Patients must be randomized (Step 2) within 32 weeks after the start of systemic therapy.

Rev. 7/12 **NOTE:** Patients may not be randomized (Step 2) less than 16 weeks after the start of systemic therapy.

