5.1.2 Local Therapy Treatments (Step 2: Arms A and B)

5.1.2.1 Arm A: Continued Systemic Therapy

Systemic therapy will continue as directed by the treating physician.

Local therapy should be offered to patients only if needed for palliation of symptoms such as tumor ulceration, pain, bulky adenopathy causing arm symptoms, and other similar situations where therapy is designed specifically to address symptoms at the local site. It may consist of radiotherapy alone, surgery alone, or the combination.

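### Section 4.2 puts the 32-week limit on the start of Step 2 treatment, which conflicts with the 10 weeks after randomization allowed for Arm B surgery

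*Combined protocol and SAP*

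**What the plan says.** Three rules bear on when Arm B surgery may take place.

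- **Randomization.** Schema item 3 and the Section 3 note: "Patients must be randomized (Step 2) within 32 weeks after the start of systemic therapy". Section 3.2.1: "Date of randomization must be within 32 weeks of initiation of optimal systemic therapy". The first sentence of 4.2 gives the same window, weeks 16 to 32. The Section 3 note adds the lower end: "Patients may not be randomized (Step 2) less than 16 weeks after the start of systemic therapy".
- **Surgery.** Schema item 6 and 5.1.2.2: "Surgery is to occur no later than 10 weeks after randomization". Neither mentions week 32.
- **Start of Step 2 treatment.** The second sentence of 4.2 forbids Step 2 treatment before randomization and then says that it "must start after completion of at least 16 weeks of systemic therapy and no more than 32 weeks from start of systemic therapy".

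The protocol does not formally define Step 2 treatment. The heading of 5.1.2 is the nearest thing to a definition: "Local Therapy Treatments (Step 2: Arms A and B").

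**The concern.** The same number, 32 weeks, limits one event in four places and a later event in a fifth. If Step 2 treatment in Arm B is surgery, 4.2 removes some or all of the time that 5.1.2.2 grants, and removes most from patients randomized latest. Late randomization is a path the protocol provides for: schema item 2 and 5.1 accept registration up to week 30, and such a patient can be randomized only in weeks 30 to 32.

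This timing rule governs delivery of the experimental treatment. Two sites, or a site and an auditor, could read different sections and classify the same operation differently. A site that took 4.2 literally might rush an operation, or withhold one because the date had passed. Withheld surgery would be non-compliance of the kind for which 8.4 makes allowance.

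**Working it through.** No sample size or power figure is involved, so the check is calendar arithmetic on the stated limits.

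**Inputs.** Randomization at week r, with 16 ≤ r ≤ 32 (schema item 3, Section 3 notes, 3.2.1, 4.2 first sentence). Surgery within 10 weeks of randomization (schema item 6, 5.1.2.2). Start of Step 2 treatment by week 32 (4.2 second sentence). All weeks count from the start of systemic therapy.

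**Latest surgery.** Under 5.1.2.2: 32 + 10 = week 42. Under 4.2: week 32. The largest gap is 10 weeks.

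**Surgery window.** Under 5.1.2.2 it is always 10 weeks. With both rules in force it is w(r) = min(10, 32 − r).

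| Week of randomization r | Window under 5.1.2.2 | Window with 4.2 also applied |
|---|---|---|
| 16 to 22 | 10 | 10 |
| 24 | 10 | 8 |
| 26 | 10 | 6 |
| 28 | 10 | 4 |
| 30 | 10 | 2 |
| 32 | 10 | 0 |

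**Where the rules part.** 32 − 10 = 22, so the full 10 weeks survive only for randomization by week 22. The rules differ over 32 − 22 = 10 of the 32 − 16 = 16 weeks of the window. That is a share of the calendar window, not of patients; the documents give no distribution of randomization times.

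**Example.** A patient is randomized at week 30 and operated on at week 36. That is 6 weeks after randomization, within the 10 weeks of 5.1.2.2, and 36 − 32 = 4 weeks late under 4.2.

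**Does Step 2 treatment mean surgery?** The sentence says that Step 2 treatment may not precede randomization, so it treats the two as separate events. Section 4.3 also separates being randomized from receiving the assigned treatment. The 5.1.2 heading describes Step 2 as local therapy. Systemic therapy is already running before randomization, so its continuation is a poor candidate for something that must not start until then.

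**The case against.** The strongest objection is that Step 2 treatment is undefined and may just mean entry to Step 2. The sentence sits in the randomization section, repeats the 16 and 32 of the sentence before it and does not distinguish the arms. The Arm A entry under 5.1.2 is continued systemic therapy. Read as local therapy in both arms, the sentence would also require Arm A palliative treatment by week 32, which cannot be intended because that treatment waits for symptoms. So the sponsor may well have meant only to restate the randomization window. That is a fair account of the intention, but it does not rescue the wording: a site reading it for Arm B finds a treatment deadline, and the same edit is right on either reading.

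It is also true that two upper limits can both be met by using the earlier one. This works for most randomization weeks, becomes tight near week 30 and fails at week 32.

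A reader might infer three stronger things, which the documents do not support.

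- **That the 16-week minimum in 4.2 shuts out patients who stopped for toxicity.** Section 3.2.2.1 says that if "at least 12 weeks of therapy have been delivered, then the patient remains eligible", and 4.2 does not repeat the exception. But 3.2.2 has the same minimum with the exception directly beneath it, its note counts the end of the treatment cycle, and 4.2.4 refers sites to Section 3 for eligibility. A real conflict needs a patient off every systemic agent, and the Section 3 note counts broadly: "Induction systemic therapy includes chemotherapy, endocrine therapy, bone-specific agents, and biologic therapy".
- **That 5.6 sets a further deadline** by placing surgery and radiation immediately after randomization. It is narrative text on duration, gives no number and refers to treatment as specified in the protocol.
- **That power is lost.** The primary analysis is by intention to treat, on survival from randomization. An operation within 10 weeks of randomization costs it nothing, whatever 4.2 says. The deviation definitions in 5.3.9 concern radiotherapy only, so they do not grade late surgery either.

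**Conclusion.** The inconsistency is real and lies in the current text. For Arm B patients randomized after week 22, 4.2 and 5.1.2.2 give different surgery deadlines, up to 10 weeks apart, and a patient validly randomized at week 32 has no surgery window under 4.2. This rests on reading Step 2 treatment in Arm B as surgery, the most natural reading though not a stated definition.

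The consequences are inconsistent deadlines, avoidable deviations and possible non-delivery of surgery to late-randomized patients. The number affected cannot be derived from the documents and may be zero. Sample size, alpha and power are not in question. The sentence should be corrected because it is an operative rule on the experimental treatment, but it is not a flaw in the analysis.

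**What to change.** Replace the second sentence of 4.2 with:

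> *No Step 2 treatment may be given before randomization. In Arm B, surgery must take place within 10 weeks of randomization (5.1.2.2), including when that date falls after week 32.*

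The first sentence of 4.2 already carries the randomization window, so nothing is lost there. The 16-week minimum and its toxicity exception then rest on 3.2.2 and 3.2.2.1 alone.

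This adopts limits stated elsewhere. The revision marks point the same way: the 32-week randomization note in Section 3 is marked 7/13 and 3.2.1 is marked up to 4/15, while 4.2 is marked 7/12. The marks do not show what changed, so the sponsor should confirm that surgery after week 32 is acceptable.

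As optional tidying, the word *immediately* in 5.6 could become a reference to 5.1.2.2 and 5.3.

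The cost is one replaced sentence in an amendment. Eligibility, sample size, monitoring boundaries and data collection do not change.
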